19.10. Data Collection

ROCSS-EX will collect data from trial entry into the original ROCSS trial until the date the ROCSS-EX follow-up is completed.

Data will be collected from two sources:

- The first is routinely collected electronic health records (or paper records if electronic records are unavailable) that local collaborators will access. This will include the number of hospital admissions related to either the stoma site or abdominal symptoms, the number of interventions in relation to symptoms and pathology at the stoma closure site.
- The second source of data will be the participant. Telephone interviews will collect participant reported information including the use the EQ-5D-5L and HerQLes tool. A standardised telephone script has been developed for collaborators to use during the telephone call.

The data gathered will be uploaded directly into a secure ROCSS-EX REDCap database hosted at the University of Birmingham by the local team. Worksheets to aid the collation may be used prior to upload. All local collaborators will receive trial specific training that will include the delivery of the telephone follow-up.

19.10.1. Case Report Form (CRF) Completion

Data reported on each form will be consistent with the source data and any discrepancies will be explained. All missing and ambiguous data will be queried. Staff delegated to complete CRFs will be trained to adhere to the ROCSS-EX guide on CRF completion.

For the ROCSS-EX, CRFs will be an electronic record completed at site, only by those at site delegated the task of doing so. Forms will be considered "complete" once all data fields have been either completed unambiguously or it has been made explicit that the data is unobtainable.

In all cases it remains the responsibility of the site's PI to ensure that the CRF has been completed correctly and that the data are accurate.

19.10.2. Source Data

Source data is defined as all information in original records and certified copies of original records of clinical findings, observations, or other activities in a clinical trial necessary for the reconstruction and evaluation of the trial. In order to allow for the accurate reconstruction of the trial and clinical management of the subject, source data will be accessible and maintained.

Data	Source
Participant Reported Outcomes (EQ-5D-5L and HerQLes)	The interview administration EQ-5D-5L and HerQLes is the source, obtained by interview directly with the participant for transcription onto the CRF, in which case the CRF is source data.
Clinical event data	The original clinical annotation is the source document. This may be found on clinical correspondence, or electronic or paper participant records. Clinical events reported by the participant, either in or out of clinic (e.g. phone calls), must be documented in the source documents. Information will be transcribed onto CRFs.
Health Economics data	Obtained by (1) interview directly with the participant for transcription onto the CRF in which case the CRF is source data. (2) To the medical record in which case the original clinical annotation is the source document. Information will be transcribed onto CRFs.
Drop out	Where a participant expresses a wish to withdraw, the conversation must be recorded in the medical records.

19.11. Statistical Analysis

Power calculation

There were 790 participants randomised in the ROCSS trial (394 in Mesh arm, 396 in No Mesh arm). Of these, 98 participants (49 in Mesh arm, 49 in No Mesh arm) have either died, did not have the stoma reversed, withdrew from the trial or were recruited from international sites. Accounting for these, 692 participants (345 in Mesh arm, 347 in No Mesh arm) remain that can be approached. Allowing for 15% dropout, it is anticipated data at 5-8 years follow-up will be obtained for approximately 588 participants (293 in Mesh arm, 295 in No Mesh arm).

The primary outcome for this study is the HerQLes quality of life score. With 588 participants expected to provide data for this, there will be over 85% power to detect an effect size of 0.25 standard deviations (two-sided alpha of 0.05). To detect a difference of 0.3 standard deviations (two-sided alpha of 0.05), with 588 participants there will be over 95% power.

Analysis methods

A separate Statistical Analysis Plan will be produced and will provide a more comprehensive description of the planned statistical analyses. A brief outline of these analyses is given below.

All analyses (primary and secondary outcomes) will be by intention-to-treat (ITT). All estimates of differences between groups will be presented with two-sided 95% confidence intervals, unless otherwise stated. P-values will be reported from two-sided tests at the 5% significance level.

The data for the primary outcome is continuous and therefore will be summarised using the mean and standard deviation along with minimum and maximum values with respect to the intervention arms and overall. The primary outcome will be analysed using a linear regression model and an adjusted mean difference and 95% confidence interval will be estimated from the model.

The secondary outcomes consist of continuous, binary and count data types. For all secondary outcomes that are continuous in nature, they will be analysed using the same statistical method as described for primary outcome.

For those secondary outcomes that are binary in nature, data will be summarised as number and percentage of participants in each category by intervention arm. An adjusted relative risk and 95% confidence interval will be estimated from a log-binomial regression model. For those secondary outcomes that are count data type, these will be analysed using a Poisson regression model (or negative binomial regression if there is evidence of overdispersion) with an offset for the length of time the participant was in the trial included in the model, to obtain an adjusted incidence rate ratio (IRR) and 95% confidence interval.

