4.2. Secondary Objectives

The secondary objectives of the ROCSS trial are to:

- Assess radiological hernia rates at one year post randomisation.
- Assess surgical re-intervention rates.
- Assess the frequency of wound infections and seroma associated with the mesh.
- Assess the impact of the mesh on a patient's quality of life and any pain experienced. Quality
 of life is an important secondary outcome measure, as the re-operation rate may be low, as
 even if a clinical hernia is diagnosed, the decision for surgical re-intervention has to take into
 account the patient's age, any co-morbidities and patient preference.
- Determine the cost effectiveness of the mesh insertion in stoma site closure and management of subsequent hernias.
- Conduct an exploratory analysis to investigate the CT scan as an early surrogate marker of late clinical herniation. Radiological hernia rate at one year post randomisation will be compared with the clinical hernia rate at two years to assess the value of using a CT scan as an early diagnostic tool of herniation. This will identify to other investigators that this is a potential area of clinical need and allow earlier reporting of future studies.

5. Outcome Measures

The outcome measures of the phase III trial will be:

Primary outcome

1. Rate of clinically detectable hernias at two years post-randomisation.

Secondary outcome measures

- 1. Radiological hernia rate at one year post-randomisation. An exploratory analysis will also compare radiological hernia rate at 1 year with clinical hernia rate at 2 years to assess the value of using a CT scan as an early diagnostic tool of incisional hernias.
- Incidence of developing a symptomatic hernia evaluated at 12 and 24 months postrandomisation. The clinical detection of hernias defined by palpable fascial defects, and global weaknesses around closed stoma sites without palpable fascial defects, will be recorded. Patient-reported hernia symptoms including a local lump or pain at the site of the stoma closure will also be collected.
- 3. Surgical re-intervention rates at 2 years post-randomisation.
- 4. Surgical complications, including wound infections at 30 days post-operatively and at 1 year post-randomisation, and seroma formation at 1 year post-randomisation.
- 5. Quality of life assessed using EuroQol EQ-5D at baseline, 30 days post-operatively, 12 and 24 months post-randomisation.

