13.2. Statistical Data Analysis

The primary outcome measure is the clinical hernia rate at 2 years. The number of clinical hernias at 2 years in the two treatment groups (biological mesh and control) will be compared using a chisquared test. Treatment effects will be expressed as a relative risk with 95% confidence interval. Any categorical secondary outcome measures (e.g. radiological hernia rate, re-operation rate, infection rates) will be analysed in the same way as the primary outcome. Continuous data (e.g. EuroQoL EQ-5D, pain scores) will be analysed using an independent 2-sample t-test (or the non-parametric equivalent as appropriate) at each time point, with the 2 year data considered the main analysis time point. Since data is being collected over multiple time points, longitudinal plots of the continuous data will be produced for visual presentation of the data, and a repeated measures analysis will be performed across all time points.

All analyses will be intention to treat, whereby patients will be analysed according to the treatment group to which they were randomised regardless of whether they complied with this treatment. All p-values will be 2-tailed and a p-value of <0.05 will be considered statistically significant.

The only planned subgroup analyses with be to compare the effect of biological mesh depending on stoma site (ileostomy or colostomy); surgical incision (reopening of midline wound or stoma site only); and skin closure type (primary or secondary). Subgroup analyses will employ a test of interaction to explore whether there is evidence that the treatment effects differ across subgroups. As with all subgroups analyses these will be interpreted with caution, and will be considered hypothesis generating.

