19.4. Outcome measures

Primary:

Quality of life at 5 to 8 years following closure of stoma site comparing participants who had mesh reinforcement of their abdominal wall with participants that had a standard closure. This will be assessed using the HerQLes tool^{17,18}.

Secondary: (all at 5-8 years follow-up)

- Participant reported incisional hernia rate
- Number of hospital visits for any hernia related reason
- Number of interventional procedures related to the stoma closure site or hernia
- Longitudinal QoL assessed using EQ-5D
- Cost analysis for all additional hernia related events

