19.7. Choice of QoL measures

A hernia-related quality of life measure will be included to provide more hernia specific information that will allow a better measure of the impact both to the patient and also to inform the cost-effectiveness analysis. The HerQLes tool was specifically designed to evaluate QoL in patients undergoing abdominal wall repair^{17,18}, such as a stoma closure. It contains 12 items, and can be used

both before and after surgery, focusing on abdominal wall function. Each of the 12 questions relate to the patient's abdominal wall function which means that it will be relevant to patients with and without a hernia (such as the ROCSS participant population). It will therefore be possible to use the same tool in both groups i.e. those who had mesh at the time of stoma closure and those who did not, and for participants with and without a hernia.

The HerQLes quality of life survey was not available when ROCSS was developed and so was not used for the original trial. Therefore, we do not have before and after scores to compare. However, the scores can be compared across groups of participants and it is known (from the original ROCSS data and our follow-up data) whether participants have had mesh inserted at the time of stoma closure and whether or not they have or have had a hernia. These groups will provide us with various comparisons to make and so the following exploratory analyses will be investigated limited to the primary outcome;

- Comparison within the control group (no mesh) for those who have developed a clinical or radiological hernia during the follow up period to those without a hernia. This will show the effect that having an incisional hernia has on a participant's quality of life.
- Comparison between the control group and the mesh group for those who did not develop a clinical or radiological hernia during the follow up period. This will show us if inserting a mesh in itself has any effect on quality of life. This has become an even more important comparison with the recent concern regarding mesh use.
- Comparison between the control group and the mesh group for those who have gone onto develop a clinical or radiological hernia. This will show us if developing a hernia despite having a prophylactic mesh inserted has a different effect on quality of life.

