The ROCSS trial originally used a non-specific QoL measure (EQ-5D). This will be repeated but evaluated as a secondary endpoint to look at longitudinal impact and provide QALY data.

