Two main analyses will be carried out to evaluate the relative cost-effectiveness of biological mesh reinforcement compared to standard closure. A cost-effectiveness analysis will be based on the cost per improvement from the HerQLes tool. In addition, a cost-utility analysis will be carried out and presented in terms of the cost per additional quality adjusted life-year (QALY) gained. QALYs are multidimensional in that they incorporate both the participants' survival and quality of life. The EQ-5D-5L will be administered as part of the telephone follow-up to derive the additional QALY in the two trial arms. The EQ-5D-5L data will be converted using the EQ-5D-3L crosswalk algorithm and UK tariff values will be applied to generate QALYs. As per the original analysis, QALYs will be calculated using the under-the-area curve method. Costs and QALYs will be discounted at an annual rate of 3.5% as per NICE guidelines.

As participants entered the original trial at different time points and the data collection for the extended follow-up study will take place at a fixed time point, the cost and QALY information will be censored. The analysis will use methods such as inverse probability weighting to take into account the censored nature of the data for the cost-utility analysis.

The total costs and consequences of the interventions will be compared using an Incremental Costeffectiveness Ratio (ICER). For the cost-utility analysis, a threshold of £30,000 per additional QALY gained will be used to assess cost-effectiveness. For the cost-effectiveness analysis, there is no benchmark on the decision maker's willingness to pay for an improvement in the HerQles tool.

The results of these economic analyses will be presented using cost-effectiveness acceptability frontiers to reflect decision uncertainty across different thresholds of willingness-to-pay per additional unit of outcome. Deterministic and probabilistic sensitivity analyses will be undertaken to explore the robustness of the findings to plausible variations in key assumptions and analytical methods used. A

scenario analysis will explore one-off quality of life decrements from the retrospective adverse events from managing hernias (e.g. hospital readmission, reoperation). These retrospective adverse events are likely to impact on participant's quality of life but the gap in data collection has meant that this impact may not be captured.

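### EQ-5D is defined as a longitudinal outcome in ROCSS-EX, but section 19.11 gives it the single-time-point regression written for HerQLes

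*Protocol*

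**What the plan says.** Protocol section 19.4 lists as a secondary outcome "Longitudinal QoL assessed using EQ-5D". Section 19.7 gives EQ-5D two purposes: "This will be repeated but evaluated as a secondary endpoint to look at longitudinal impact and provide QALY data".

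The earlier measurements are set out in section 5 (Outcome Measures): "Quality of life assessed using EuroQol EQ-5D at baseline, 30 days post-operatively, 12 and 24 months post-randomisation". Section 19.10 adds the EQ-5D-5L by telephone at 5-8 years.

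For the analysis, section 19.11 says the primary outcome, HerQLes, will be "analysed using a linear regression model and an adjusted mean difference and 95% confidence interval will be estimated from the model". It then says: "For all secondary outcomes that are continuous in nature, they will be analysed using the same statistical method as described for primary outcome". The covariates behind the adjustment are not named. Section 19.11 describes itself as an outline and leaves fuller detail to a separate SAP.

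On HerQLes, which was not used in the original trial, section 19.7 states: "Therefore, we do not have before and after scores to compare".

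Two other places bear on the point. For continuous outcomes in the original trial, including EQ-5D, section 13.2 says "a repeated measures analysis will be performed across all time points". For the economic analysis, section 19.12 says "The EQ-5D-5L data will be converted using the EQ-5D-3L crosswalk algorithm", applies UK tariff values and computes QALYs by area under the curve.

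**The concern.** The method was chosen for an instrument measured once, and a cross-reference then extends it to an instrument measured five times. A regression of a single score cannot describe how the arms differ over time, which is what the outcome's label and section 19.7 promise.

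Three things are at stake:

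- The longitudinal outcome is not estimated by the analysis assigned to it.
- Participants with no 5-8 year EQ-5D drop out of that analysis, although they may have a baseline and up to three follow-up values.
- If baseline EQ-5D is not among the covariates, the 5-8 year contrast is less precise than the data allow.

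EQ-5D is a secondary outcome, but long-term quality of life is the research question of ROCSS-EX (sections 19.1 and 19.2).

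**Working it through.** **Which outcomes the sentence governs.** Of the five secondary outcomes in section 19.4, the participant-reported hernia rate is binary. Hospital visits and interventional procedures are counts, and section 19.11 gives each of these types its own model. The cost analysis belongs to section 19.12. That leaves EQ-5D as the only listed continuous secondary outcome, so the sentence on continuous secondary outcomes is in effect the EQ-5D analysis.

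**What that model delivers.** One score per participant, one regression, one adjusted mean difference. Naming baseline EQ-5D as a covariate in the SAP would sharpen the 5-8 year contrast. It would not bring in the 30-day, 12-month and 24-month values as outcomes, and it would not yield an arm-by-time effect.

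**The plan's own figures (section 19.11).** Participants who can be approached: 394 − 49 = 345 and 396 − 49 = 347, total 692. With 15% dropout, 692 × 0.85 = 588 (293 and 295 per arm), so about 692 − 588 = 104 are expected to have no 5-8 year value.

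The SE of the difference in SD units is √(1/293 + 1/295) = 0.0825. Power at two-sided alpha 0.05 is Φ(δ/SE − 1.96):

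- δ = 0.25 SD: 85.8% (noncentral t: 85.7%). The protocol says over 85%.
- δ = 0.30 SD: 95.3%. The protocol says over 95%.

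Both stated figures reproduce. They refer to HerQLes; the protocol states no power for EQ-5D.

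**Effect of adjusting EQ-5D for its baseline.** Let ρ be the correlation between baseline and 5-8 year EQ-5D. The protocol does not give it, and 0.3 to 0.7 is assumed. Adjustment multiplies the variance by 1 − ρ², so SE = 0.0825 × √(1 − ρ²). The equivalent unadjusted sample is 588/(1 − ρ²). Applying the protocol's 588 to EQ-5D:

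| ρ | Variance factor | SE (SD units) | 95% CI half-width (SD units) | Power at 0.25 SD | Equivalent unadjusted N |
|---|---|---|---|---|---|
| none | 1.00 | 0.0825 | 0.162 | 85.8% | 588 |
| 0.3 | 0.91 | 0.0787 | 0.154 | 88.8% | 646 |
| 0.5 | 0.75 | 0.0714 | 0.140 | 93.8% | 784 |
| 0.7 | 0.51 | 0.0589 | 0.115 | 98.9% | 1153 |

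Read the other way, omitting baseline makes the variance 1/0.91 = 1.10 to 1/0.51 = 1.96 times as large, that is 10% to 96% larger. These figures cover the baseline covariate only. Whatever a mixed model gains by using the interim visits of participants without a 5-8 year value is not quantified here.

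**The case against.** The strongest reply is that section 19.11 is an outline, the model is already an adjusted one, and covariates and repeated-measures details commonly sit in the SAP. This stands for the covariates: baseline EQ-5D may well be among them, and leaving the list open is not an error. It does not stand for the model. The protocol states a method for this outcome, and that method is not longitudinal whatever covariates are added.

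A reader might infer that the earlier EQ-5D data go unused altogether. The documents do not support that. Section 15.1.2 says the values from baseline to 24 months were collected so that QALYs can be calculated, section 19.12 extends the area-under-the-curve calculation, and section 13.2 planned a repeated measures analysis of the original trial's visits. What is missing is a longitudinal model that reaches the 5-8 year visit.

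A reader might also infer that two EQ-5D scales will be mixed. Section 19.12 converts the 5L responses to the 3L by crosswalk with UK tariff values, and no other value set is proposed. Section 19.11 simply does not say which index it uses, so this is a risk that a cross-reference removes.

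Finally, a mixed model is not free of assumptions. It uses the information from participants without a 5-8 year value validly only if those values are missing at random given what was observed.

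**Conclusion.** The point holds in a limited form. Sections 19.4 and 19.7 define a longitudinal EQ-5D outcome with a purpose beyond QALYs, and section 19.11 assigns it a model that estimates one difference at one time. Within ROCSS-EX, the interim values enter only through the QALYs of section 19.12. The repeated measures approach of section 13.2 has been dropped for this outcome with no reason given.

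The gain from correcting this is an answer to the stated outcome, plus precision. For the baseline covariate, the variance factor is 0.91 to 0.51, and power at 0.25 SD with 588 participants goes from 85.8% to about 89-99%. This rests on the assumed correlation of 0.3 to 0.7 and on carrying the HerQLes sample over to EQ-5D. If the SAP already adjusts for baseline EQ-5D, that part of the gain is already secured and only the longitudinal gap remains.

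Two stronger readings do not follow. Omitting baseline does not bias the comparison: the arms were randomised, and chance imbalance is a matter of precision. The sample size and power statements are not wrong either: they concern HerQLes, and they reproduce.

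**What to change.** In section 19.11, except EQ-5D from the sentence on continuous secondary outcomes and state its own analysis. Use a linear mixed (repeated-measures) model with follow-up at 30 days, 12 months, 24 months and 5-8 years as the outcome. Include arm, visit and arm by visit, with baseline EQ-5D and the three minimisation variables (stoma type, surgical incision, skin closure type) as covariates. Report the 5-8 year contrast with its 95% confidence interval. State that the crosswalked index of section 19.12 is used at the 5-8 year visit, and that the model assumes data are missing at random.

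The cost is about two sentences and a little more analysis work. The data are already held or are collected under the current plan, and no sample size or power figure needs to change. The change should be made before the analysis that section 19.14 schedules for spring-summer 2021.

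Two further steps are optional and correct no error: adding baseline EQ-5D and baseline pain as covariates in the HerQLes model, and adjusting the QALY difference for baseline utility.
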